6.2.10 Measurable or non-measurable disease per RECIST criteria v1.1

6.2.11 ECOG performance status 0-1

6.2.12 Adequate organ function, as defined by all of the following:

- Hematologic parameters:
 - Absolute neutrophil count (ANC) $\geq 1500/\mu\text{l}$ (without growth factor support)
 - Platelets $\geq 100,000/\mu\text{l}$ (no transfusion allowed within 2 weeks)
 - Hemoglobin ≥ 9.0 g/dl (may be reached by transfusion)
- Liver function:
 - Serum bilirubin ≤ 1.5 x upper limit of normal (ULN) unless attributable to Gilbert's syndrome
 - AST ≤ 2.5 x ULN, or ≤ 5 x ULN if liver metastases are present
 - ALT ≤ 2.5 x ULN, or ≤ 5 x ULN if liver metastases are present
- Kidney function:
 - Creatinine ≤ 1.5 ULN

- Endocrine function:
 - Fasting plasma glucose <140 mg/dl (may be on antiglycemic agents other than insulin). Fasting glucose measurement must be obtained at least 8 hours after the most recent caloric intake.

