12.1 CRITERIA FOR THERAPEUTIC RESPONSE/OUTCOME ASSESSMENT

The primary objective of this study is to determine the recommended phase II dose of BYL719 when administered in combination with either letrozole or exemestane. As of January 2014, this trial is being amended such that an additional primary objective is to determine the recommended phase II dose of BYL719 administered in a 7 day on, 7 day off schedule, in combination with letrozole, and the recommended phase II dose of BYL719 administered on a 5 day on, 2 day off schedule, in combination with exemestane. All patients who receive at least one dose of BYL719 will be evaluable for toxicity assessment. See Section 9.3 for the definitions of dose limiting toxicities and Section 9.4 for the dose-finding schema.

In order to estimate the efficacy of BYL719 plus letrozole or exemestane (a secondary endpoint), we will calculate the following for each arm separately in the expansion cohort only:

- a. Progression-free survival (PFS) will be examined using Kaplan-Meier methods.
- b. Overall response rate (ORR = complete response (CR) plus partial response (PR)) will be calculated with an exact confidence interval.
- c. Clinical benefit rate at 16 weeks (CBR = CR + PR + stable disease) will be calculated with an exact confidence interval.
- d. Time to treatment failure (TTF) will be examined using Kaplan-Meier methods.

The RECIST criteria version 1.1 will be used to evaluate therapeutic response. All patients who receive at least one week of BYL719 in combination with letrozole or exemestane will be evaluable for response. Patients with measurable or non-measurable lesions are included in this study. Measurable lesions are defined as those that can be measured accurately in at least one diameter, that is ≥ 20 mm using conventional imaging techniques (including incremental CT) or ≥ 10 mm using spiral CT equipment. Non-measurable lesions include bony metastases, leptomeningeal disease, ascites, pleural/pericardial effusions, inflammatory breast cancer, lymphangitic carcinomatosis, and heavily calcified and cystic/necrotic lesions.

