14.3 Expansion Phase

In the expansion portion of the study, 10 additional patients will be enrolled in each arm, Arm C and Arm D, in order to further define the safety and feasibility of BYL719 in combination with letrozole or exemestane at the established dose from the dose-finding phase, and to estimate the efficacy of this combination.

In order to help ensure that the DLT rate observed among the additional 10 patients in each arm is consistent with the DLT rate observed at the established dose from the dose-finding portion, the following decision rule will be implemented for each of the two study arms. If ≥ 4 DLTs are seen at any time in any one expansion arm, then it is likely that the safe and tolerable dose determined during the first portion of the trial is too toxic. The safety data will then be reviewed with the primary investigator and Novartis to determine how to move forward. Depending on the circumstances, we may consider de-escalating the dose of BYL719 to the next lower dose level and accruing 10 additional patients at that level. The probability of observing at least 4 patients with a DLT in the 10 additional patients is .28 if 1 of 6 patients were seen with a DLT in the dose-finding phase of the study. The probability of observing at least 4 patients with a DLT in the 10 additional patients is .09 if 0 of 6 patients were seen with a DLT in the dose-finding phase of the study.¹¹ The below table provides additional details on the probability of observing at least 1 to 9 patients with DLTs in the expansion cohort of 10 patients given that 0 or 1 patient in the initial dose-finding cohort of 6 patients had a DLT.¹¹

DLTs in dose-finding cohort	DLTs in expansion cohort								
	1 DLT (of 10)	2 DLTs	3 DLTs	4 DLTs	5 DLTs	6 DLTs	7 DLTs	8 DLTs	9 DLTs
0 (of 6)	0.59	0.33	0.18	0.09	0.04	0.02	0.01	<0.01	<0.01
1(of 6)	0.85	0.64	0.44	0.28	0.16	0.08	0.04	0.01	0.01

The two arms of the study will be monitored in tandem, and we have added an overall sequential global stopping rule to be applied as both expansion cohorts are accruing. We include this early stopping rule across both arms because the mechanism and toxicities of both AIs are known to be very similar. Our global stopping rule is based on repeated significance testing and serves as a global safety measure. We assume a grade 4 toxicity rate of 10% as acceptable and 35% as unacceptable. With these assumptions, if 2 of the

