14.4 Secondary Objectives

There are several planned secondary analyses. Selected non-hematologic and hematologic toxicities will be described, as measured by the NCI Common Toxicity Criteria, version 4.0, with the maximum grade over all cycles used as the summary measure per patient.

In order to estimate the efficacy of BYL719 plus letrozole or exemestane, we will calculate the following for each arm, Arm C and Arm D separately in the expansion cohort only:

- a. Progression-free survival (PFS) will be examined using Kaplan-Meier methods.
- b. Overall response rate (ORR = complete response (CR) plus partial response (PR)) will be calculated with an exact confidence interval.
- c. Clinical benefit rate (CBR = CR + PR + stable disease at 16 weeks) will be calculated with an exact confidence interval.
- d. Time to treatment failure (TTF) will be examined using Kaplan-Meier methods.

Pharmacokinetic parameters such as AUC and C_{max} of daily BYL719 will be calculated.

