Based on our ongoing experience with our tumor biopsy study to evaluate molecular mechanisms of resistance in patients with HER2+ disease (MSKCC IRB # 06-163, [name] - PI), we anticipate that it will be feasible to obtain a pre-treatment biopsy in at least 80% of patients (~30 patients assuming total accrual of 38 patients). Due to logistical issues, such as lack of sufficient viable cells in the biopsy sample, it is possible that a viable pre-treatment biopsy sample may not be obtained in several patients.

In order to determine if pharmacodynamic markers of PI3K pathway hyperactivation and inhibition predict for PFS, proteomic analysis of pre-treatment and Day 15 on-treatment biopsies will be performed. The Spearman's rank correlation of inpatient percent change in PI3K pathway activation signature (measured as a continuous variable) with percent tumor volume change at 8 week CT scan (measured as a continuous variable) will be calculated to evaluate whether pharmacodynamic markers of PI3K pathway inhibition are predictive of response to therapy.

We anticipate that it will be feasible to obtain a Day 15 on-treatment biopsy in at least 50% of patients (~19 patients assuming total accrual of 38 patients).

To evaluate mechanisms of AI resistance, the analysis will include pre-treatment tumor biopsies obtained in patients who had POD on an AI at the time of study consent, on-treatment biopsies, as well as optional post-progression biopsies. We estimate that this will include about half of patients in the dose-finding phase (because those with stable disease will be excluded), and all patients in the expansion phase who have a viable pre-treatment biopsy sample.

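### The single ORR per expansion arm counts patients with only non-measurable disease, who can be responders only through a complete response, so the rate depends on case mix

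*Combined protocol and SAP*

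**What the plan says.** Inclusion criterion 6.2.10 reads "Measurable or non-measurable disease per RECIST criteria v1.1", and Section 12.1 repeats the point: "Patients with measurable or non-measurable lesions are included in this study". Section 12.1 then describes both lesion types. On the second it says "Non-measurable lesions include bony metastases, leptomeningeal disease, ascites, pleural/pericardial effusions, inflammatory breast cancer, lymphangitic carcinomatosis", among others.

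The response-evaluable set carries no measurability condition. Section 12.1 states "All patients who receive at least one week of BYL719 in combination with letrozole or exemestane will be evaluable for response", and Section 14.2 repeats this rule.

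The criteria are fixed in Section 12.1: "The RECIST criteria version 1.1 will be used to evaluate therapeutic response". Section 14.4 gives the endpoint: "Overall response rate (ORR = complete response (CR) plus partial response (PR)) will be calculated with an exact confidence interval". Both sections calculate it for each arm separately and in the expansion cohort only. Section 14.3 sets the size: "10 additional patients will be enrolled in each arm, Arm C and Arm D".

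Neither section names a denominator restricted to measurable disease. Neither says how a patient with only non-measurable disease is classified for ORR or for clinical benefit at 16 weeks, where the only categories are CR, PR and stable disease.

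**The concern.** Section 12.1 separates measurable from non-measurable lesions, but no analysis uses the distinction. Partial response under RECIST 1.1 is a fall in the measured size of target lesions. A patient whose disease is confined to bone or effusions has no such lesion, so the PR half of the numerator is closed to her while she still adds one to the denominator.

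Such patients are expected. Sections 10.4.6 and 10.12 have a separate biopsy rule for bone-only metastases, and Section 10.9 refers to bone-only disease when setting bone-scan rules.

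In a cohort of 10, each such patient lowers the highest attainable PR rate by 1/10, or 10 percentage points. The reported ORR then mixes drug activity with enrolment mix. If the denominator is left unstated, it could also be narrowed after the responses are known.

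**Working it through.** **Inputs from the documents.** Expansion size is 10 per arm (14.3). ORR is CR + PR with an exact interval (12.1, 14.4). The evaluable set is everyone with one week or more of the combination (12.1, 14.2). The plan gives no expected ORR, target or power for this endpoint, so there is no stated figure to reproduce.

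**Assumed inputs.** The share *m* of evaluable patients with only non-measurable disease is not in the documents; I use 10% to 40%. The response rate *p* in measurable patients is also assumed, at 30%, with 20% and 40% as alternatives. The CR rate *c* in non-measurable-only patients is set to 0 and then varied. The documents name RECIST 1.1 without reproducing its definition of partial response; I take it as a measured fall in target lesions.

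**Step 1: expected ORR under the plan's rule.** Expected ORR = p(1 - m) + c·m. With c = 0:

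| p | m = 10% | m = 20% | m = 30% | m = 40% |
|---|---|---|---|---|
| 20% | 18% | 16% | 14% | 12% |
| 30% | 27% | 24% | 21% | 18% |
| 40% | 36% | 32% | 28% | 24% |

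For p = 30% the products are 0.30 × 0.9 = 0.27, 0.30 × 0.8 = 0.24, 0.30 × 0.7 = 0.21 and 0.30 × 0.6 = 0.18.

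**Step 2: effect of the CR assumption.** The shortfall is (p - c)·m. With p = 30%, m = 30% and c = 10%, expected ORR is 0.30 × 0.7 + 0.10 × 0.3 = 0.21 + 0.03 = 24%, against 21% when c = 0. If c equalled p there would be no shortfall.

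**Step 3: the same data under the two denominators.** The exact (Clopper-Pearson) 95% limits for x responders in n are the 2.5% point of Beta(x, n - x + 1) and the 97.5% point of Beta(x + 1, n - x). For two responders, both with measurable disease:

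| Non-measurable-only patients of 10 | Measurable-only ORR | Exact 95% CI |
|---|---|---|
| 0 (the plan's rule gives this row whatever the mix) | 2/10 = 20% | 2.5-55.6% |
| 1 | 2/9 = 22% | 2.8-60.0% |
| 2 | 2/8 = 25% | 3.2-65.1% |
| 3 | 2/7 = 29% | 3.7-71.0% |
| 4 | 2/6 = 33% | 4.3-77.7% |

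**The case against.** The strongest defence is that the secondary objective in Section 2.2 concerns patients with HR+ locally advanced or metastatic disease, not only those with measurable lesions, so an all-evaluable rate answers the question asked. PFS, clinical benefit and time to treatment failure are reported beside it and do not need a partial response. At n = 10 the intervals in the working overlap almost entirely, so sampling error exceeds the dilution. No decision rests on ORR: the expansion rules in Section 14.3 use DLTs and grade 4 toxicity.

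Most of that stands, and it limits the weight of the point. It does not remove the point. A wide interval shows imprecision, not that the quantity estimated shifts with the enrolment mix. The all-evaluable rate can be kept; what is missing is the rate beside it.

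Four stronger readings are tempting, and the documents do not support them.

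- *The Spearman analysis has an overstated 19 pairs.* Section 14.5 says "We anticipate that it will be feasible to obtain a Day 15 on-treatment biopsy in at least 50% of patients (~19 patients", based on accrual of 38. This counts biopsies, is worded as a minimum, and is correct: 0.50 × 38 = 19. No number of biopsy and tumor-change pairs is planned. Bone-only patients already have no Day 15 biopsy (10.4.6, 10.12), so a share assumed for ORR cannot be carried over to the biopsied patients.
- *A planned comparison of Arms C and D is biased.* No such comparison is specified. Efficacy is calculated by arm, patients are not randomized (15.3), and Section 4.0 records the Arm C expansion as on hold in June 2015.
- *Non-measurable-only patients are certain non-responders.* ORR includes CR, which they can achieve.
- *Every treated patient is evaluable for response.* The rule needs one week of the combination; a single dose suffices only for toxicity.

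**Conclusion.** The point holds as a gap in the definition of a secondary endpoint. As written, patients who cannot have a partial response sit in the ORR denominator, and no rule covers their classification.

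The size cannot be fixed from the documents. A measurable-patient rate of 30% would appear as 27% at an assumed share of 10% and as 18% at 40%, a shortfall of 3 to 12 percentage points. This needs three assumptions: the share, the 30% rate, and no CR in the non-measurable-only group. Any CR in that group makes the shortfall smaller. The calculation also takes 10 evaluable patients per arm; anyone with less than a week of the combination would drop out of the denominator.

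The recommended phase II dose, the DLT rules and the global stopping rule do not use ORR and are untouched.

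**What to change.** In Sections 12.1 and 14.4:

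- Report ORR with its exact interval in patients with at least one measurable lesion at baseline, and show the all-evaluable rate beside it, with both denominators.
- Keep PFS, CBR and TTF on all evaluable patients.
- State that a non-measurable-only patient without CR or progression at 16 weeks counts as stable disease for CBR.

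The ~19 in Section 14.5 needs no correction.

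The cost is a few sentences, with a smaller denominator and a wider interval for the added rate. Sections 8.3 and 10.9 already require baseline CT and bone scan, so the measurable subset can be derived without new assessments. The documents do not say that lesion type is recorded as a data item, so some abstraction from baseline scans may be needed. Section 1.0 says accrual has closed, which does not prevent a change to an analysis definition; it should be settled before responses are tabulated.

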13.1 CRITERIA FOR REMOVAL FROM STUDY

Criteria for removal from the study are:

- Progressive disease
- Unacceptable toxicity
- Three or more consecutive weeks of a delay in treatment due to toxicities
- Intercurrent, non-cancer related illness that prevents continuation of protocol therapy or follow-up
- Major protocol violation that would render the patient inevaluable for safety/toxicity
- Repeated non-compliance by the patient with protocol requirements
- Changes in the patient's condition or study drug related toxicity such that, in the opinion of the investigator, continued participation in the protocol would compromise the patient's well-being
- Withdrawal of the patient's consent for any reason
- Termination of the clinical trial by the investigator or Novartis, the drug manufacturer

14.1 BIostatistics

This is a single institution phase I study of BYL719 in combination with letrozole or exemestane, with a dose-finding phase and an expansion phase. The primary objective is to determine the recommended phase II dose of BYL719 when administered in combination with either letrozole or exemestane to patients with HR+ locally-advanced or metastatic breast cancer. As of January 2014, this trial is being amended such that an additional primary objective is to determine the recommended phase II dose of BYL719 administered in a 7 day on, 7 day off schedule, in combination with letrozole, and the recommended phase II dose of BYL719 administered on a 5 day on, 2 day off schedule, in combination with exemestane.

This clinical trial was initially comprised of two arms, one for BYL719 in combination with letrozole (Arm A) and another for BYL719 in combination with exemestane (Arm B). As of January 2014, Arms A and B will no longer accrue patients and the study will be amended to include Arms C and D. Arm C will involve letrozole with BYL719 given on days 1-7 and 15-21 of a 28 day cycle. Arm D will involve exemestane with BYL719 given on days 1-5, 8-12, 15-19, 22-26 of a 28 day cycle. Anastrozole will not be evaluated in this study because anastrozole is a non-steroidal AI similar to letrozole. Arms C and D employ distinct aromatase inhibitors for clarity throughout clinical care. However, given the similar toxicity profile seen with both aromatase inhibitors with continuously dosed BYL719 (Arms A and B), results from either arm are felt to be generalizable to either aromatase inhibitor.

The dose-finding phase will require 4 to 24 patients for each arm that will accrue patients (Arm C and Arm D), and the expansion phase will require 10 patients for each arm. We anticipate ~38 patients total across both arms, and we estimate an accrual rate of at least 2 patients per month, with a total time of two years to complete the study.

14.2 Dose-Finding Phase

The purpose of the dose-finding portion of the study is to determine the recommended phase II dose of BYL719 in combination with a fixed dose of either letrozole or exemestane. For Arm A and Arm B, the five proposed doses of BYL719 are 200mg, 250mg, 300mg, 350mg or 400mg. For Arms C and D, the five proposed doses of BYL719 are 150mg, 200mg, 250mg, 300mg, and 350mg.

The plans for dose escalation or de-escalation consist of entering patients in cohorts of three. The specific details are given in Section 9.4. Dose-limiting toxicities are defined in Section 9.3. All patients within a cohort will be observed for toxicity for one cycle (28 days) prior to entering patients at the next dose level. If a patient discontinues study participation during the first cycle (within 28 days of starting study treatment) for reasons unrelated to an adverse event or disease progression, an additional patient may be enrolled to replace that subject. We expect this early dropout to be a rare event, occurring 5% of the time, and will be examined closely as a source for potential bias. Otherwise, all patients who receive at least one dose of BYL719 in combination with letrozole or exemestane will be evaluable for toxicity. All patients who receive at least one week of BYL719 in combination with letrozole or exemestane will be evaluable for response.

The probability that dose escalation or de-escalation will occur at any stage during this portion of the study is a function of the underlying DLT rate at the current dose level. This probability can be calculated as the sum of the binomial probabilities of the following two outcomes that would permit escalation to occur:

1. No DLT observed in the first three patients.
2. One DLT is observed in the first three patients followed by no DLT observed in three additional patients at the same dose level.

The true risk of toxicity is expected to be in the range of 10%-40%. The following table shows the corresponding probabilities of dose escalation:

True Risk of Toxicity	.10	.20	.30	.40
Probability of Escalation	.91	.71	.49	.31

These numbers show that the probability of escalating to the next dose level is large when the underlying true toxicity rate is small and the probability of escalating decreases appropriately as the true toxicity rate increases.

Between 2-6 patients will be treated at each dose level. Assuming 4 dose levels, this portion of the trial will require a minimum of 4 and a maximum of 24 patients for each arm. If 2 or more patients in the lowest dose cohort (Cohort -2 for Arms A and B, and Cohort -1 for Arms C and D) for either arm experience DLT, then we will conclude that the combination is not

feasible and will discontinue the affected arm of the trial. If this occurs, accrual onto the unaffected arm will be halted until safety data is reviewed by the primary investigator and Novartis to determine whether to continue or close the unaffected arm of the trial.

We expect both arms (Arm C and Arm D) to accrue simultaneously, as letrozole is typically given first-line for HR+ metastatic breast cancer, while exemestane is more often used in the second-line setting. With an expected accrual rate of at least 2 patients per month, it is expected that the dose-finding portion of the trial will take less than 1 year. This allows each 3-patient cohort to be observed for 28 days, the length of time for treatment with one cycle of therapy, prior to additional patients being accrued.

14.3 Expansion Phase

In the expansion portion of the study, 10 additional patients will be enrolled in each arm, Arm C and Arm D, in order to further define the safety and feasibility of BYL719 in combination with letrozole or exemestane at the established dose from the dose-finding phase, and to estimate the efficacy of this combination.

In order to help ensure that the DLT rate observed among the additional 10 patients in each arm is consistent with the DLT rate observed at the established dose from the dose-finding portion, the following decision rule will be implemented for each of the two study arms. If ≥ 4 DLTs are seen at any time in any one expansion arm, then it is likely that the safe and tolerable dose determined during the first portion of the trial is too toxic. The safety data will then be reviewed with the primary investigator and Novartis to determine how to move forward. Depending on the circumstances, we may consider de-escalating the dose of BYL719 to the next lower dose level and accruing 10 additional patients at that level. The probability of observing at least 4 patients with a DLT in the 10 additional patients is .28 if 1 of 6 patients were seen with a DLT in the dose-finding phase of the study. The probability of observing at least 4 patients with a DLT in the 10 additional patients is .09 if 0 of 6 patients were seen with a DLT in the dose-finding phase of the study.¹¹ The below table provides additional details on the probability of observing at least 1 to 9 patients with DLTs in the expansion cohort of 10 patients given that 0 or 1 patient in the initial dose-finding cohort of 6 patients had a DLT.¹¹

DLTs in dose-finding cohort	DLTs in expansion cohort								
	1 DLT (of 10)	2 DLTs	3 DLTs	4 DLTs	5 DLTs	6 DLTs	7 DLTs	8 DLTs	9 DLTs
0 (of 6)	0.59	0.33	0.18	0.09	0.04	0.02	0.01	<0.01	<0.01
1(of 6)	0.85	0.64	0.44	0.28	0.16	0.08	0.04	0.01	0.01

The two arms of the study will be monitored in tandem, and we have added an overall sequential global stopping rule to be applied as both expansion cohorts are accruing. We include this early stopping rule across both arms because the mechanism and toxicities of both AIs are known to be very similar. Our global stopping rule is based on repeated significance testing and serves as a global safety measure. We assume a grade 4 toxicity rate of 10% as acceptable and 35% as unacceptable. With these assumptions, if 2 of the

first 5 patients, 3 of the first 10 patients, 4 of the first fifteen or 5 of 20 patients accrued experience a grade 4 toxicity, we will discontinue the entire study. With this rule, the probability of discontinuing the study if the true toxicity rate is 35% is .92. If the true toxicity rate is 10%, this probability is .10.

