4.0 OVERVIEW OF STUDY DESIGN/INTERVENTION

[figure not shown]
This is a single institution phase I dose-finding study with an expansion cohort. The primary objective is to determine the recommended phase II dose of BYL719 when administered in combination with either letrozole or exemestane to patients with HR+ locally-advanced or metastatic breast cancer. As of January 2014, this trial is being amended such that an additional primary objective is to determine the recommended phase II dose of BYL719 administered in a 7 day on, 7 day off schedule, in combination with daily letrozole, and the recommended phase II dose of BYL719 administered on a 5 day on, 2 day off schedule, in combination with daily exemestane. An expansion cohort for Arms C and D will be treated at the final dose level to further define the safety and feasibility of each combination, and to estimate efficacy.

This clinical trial was initially comprised of two arms, one for daily BYL719 in combination with letrozole (Arm A) and another for BYL719 in combination with exemestane (Arm B). As of January 2014, Arms A and B will no longer accrue patients and the study will be amended to include Arms C and D. Arm C will involve letrozole with BYL719 given on days 1-7 and 15-21 of a 28 day cycle. Arm D will involve exemestane with BYL719 given on days 1-5, 8-12, 15-19, 22-26 of a 28 day cycle. The figure below shows the overall study scheme for Arms C and D. Patients will be eligible for only one of the two arms depending on which AI (letrozole or exemestane) they were taking before study enrollment. Patients will not be randomized to one of the two arms.

Dose-escalation phase

Dose-expansion phase

For both the dose-finding and expansion phases of Arms C and D, patients may have stable or progressive disease on letrozole or exemestane, and BYL719 will be added. We anticipate 12-30 patients for the dose-finding phase of the trial (6-15 patients in Arm C, and 6-15 patients in Arm D), and 20 patients for the expansion phase of the trial (10 patients in Arm C, and 10 patients in Arm D).

As of June 2015, the recommended phase II dose of BYL719 has been determined to be 350mg for Arm D and we are currently enrolling 10 patients to the corresponding arm in the expansion phase of the study. Dose Expansion to Arm C is currently on hold.

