9.6 Expansion Phase

As of June 2015, the recommended phase II dose of BYL719 has been determined to be 350mg for Arm D and we are currently enrolling 10 patients to the corresponding arm in the expansion phase of the study. The purpose of the expansion phase is to further define the safety and feasibility of BYL719 daily or intermittently in combination with letrozole or exemestane, and to estimate efficacy.

Patients will be eligible for only one of the four arms depending on which AI (letrozole or exemestane) they were taking immediately prior to study enrollment. Patients will not be randomized to one of the four arms.

In the expansion phase, BYL719 will be administered orally on the same administration schedule for that arm as for the dose-finding phase and at the dose established in the dose-finding phase of the trial. For Arm D, the established dose is 350mg for BYL719. Patients will continue on treatment until progression of disease or unacceptable toxicity.

In order to help ensure that the DLT rate observed among the additional 10 patients in each arm is consistent with the DLT rate observed at the established dose from the dose-finding portion, the following decision rule will be implemented for each of the two study arms. If ≥ 4 DLTs are seen at any time in any one expansion arm, then it is likely that the safe and tolerable dose determined during the dose-finding portion of the trial is too toxic. The safety data will then be reviewed with the primary investigator and Novartis to determine how to move forward. Depending on the circumstances, we may consider de-escalating the dose of BYL719 to the next lower dose level and accruing 10 additional patients at that level. The probability of observing at least 4 patients with a DLT in the 10 additional patients is .28 if 1 of 6 patients were seen with a DLT in the dose-finding phase of the study. The probability of observing at least 4 patients with a DLT in the 10 additional patients is .09 if 0 of 6 patients were seen with a DLT in the dose-finding phase of the study.¹¹

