The two arms of the study will be monitored in tandem, and we have added an overall sequential global stopping rule to be applied as both expansion cohorts are accruing. We include this early stopping rule across both arms because the mechanism and toxicities of both AIs are known to be very similar. Our global stopping rule is based on repeated significance testing and serves as a global safety measure. We assume a grade 4 toxicity rate of 10% as acceptable and 35% as unacceptable. With these assumptions, if 2 of the first 5 patients, 3 of the first 10 patients, 4 of the first fifteen or 5 of 20 patients accrued experience a grade 4 toxicity, we will discontinue the entire study. With this rule, the probability of discontinuing the study if the true toxicity rate is 35% is .92. If the true toxicity rate is 10%, this probability is .10.

Likewise, if two different recommended phase II doses are determined in the separate arms, safety data will be reviewed with the primary investigator and Novartis, and we will determine how to move forward. Depending on the circumstances, we will consider reducing the dose of BYL719 in the unaffected arm of the trial, if felt to be appropriate to ensure patient safety.

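### The grade 4 stopping rule's .92 stopping probability needs 20 pooled expansion patients; with Arm C expansion on hold, Arm D's 10 patients give .78, and the stated .10 does not follow from the printed boundaries.

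*Combined protocol and SAP*

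**What the plan says.** Section 14.3, repeated in 9.6, sets a global safety rule over the two 10-patient expansion cohorts, described as a "global stopping rule to be applied as both expansion cohorts are accruing". The design rates are given directly: "We assume a grade 4 toxicity rate of 10% as acceptable and 35% as unacceptable". The study is discontinued "if 2 of the first 5 patients, 3 of the first 10 patients, 4 of the first fifteen or 5 of 20 patients accrued" have a grade 4 toxicity. Of the resulting properties, 14.3 says "the probability of discontinuing the study if the true toxicity rate is 35% is .92" and "If the true toxicity rate is 10%, this probability is .10".

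Section 4.0 reports that, as of June 2015, the Arm D recommended dose had been set and its expansion was open, and adds: "Dose Expansion to Arm C is currently on hold". Section 9.6 likewise says of Arm D that "we are currently enrolling 10 patients to the corresponding arm in the expansion phase of the study". Section 14.3 still plans 10 expansion patients in each of Arms C and D. Section 1.0 records that by Amendment 13 (January 2017) accrual had closed at 51 patients, without a split by arm or phase.

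No section restates the rule, or its probabilities, for one expansion arm.

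**The concern.** The .92 is a cumulative probability over four looks. If only 10 patients are enrolled in expansion, the looks at 15 and 20 never occur, and the quoted figure overstates the rule's ability to detect an unacceptable grade 4 rate in that cohort.

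The scope of the rule is also unclear. It is described as running while both cohorts accrue, yet its boundaries count patients accrued without saying they must come from both arms. If it does not run on Arm D alone, the remaining expansion-specific trigger for that arm is the review at 4 or more DLTs. That review leads to a discussion with the manufacturer and possible de-escalation; it does not mandate a stop.

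Finally, when the rule is recomputed, the second stated figure (.10 at a 10% rate) does not come out of the printed boundaries. The pair as a whole therefore needs reconciling before any one-arm figure is quoted beside it.

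**Working it through.** **Inputs (Sections 9.6 and 14.3).** Rates p = .10 and p = .35. Stop if the cumulative grade 4 count is at least 2 at n = 5, 3 at n = 10, 4 at n = 15, or 5 at n = 20. Planned expansion is 10 + 10 = 20; with Arm C on hold it is 10.

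**Method.** Exact binomial recursion in blocks of 5. At each look, the probability of reaching the boundary is added to the stopping total, and only the lower counts are carried forward.

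**At p = .35.** In a block of 5:
- P(0) = .65^5 = .1160
- P(1) = 5 × .35 × .65^4 = .3124
- P(≥2) = .5716, P(≥3) = .2352, P(≥4) = .0540

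Look 1 (n = 5): stop = .5716. Carried forward: count 0 with .1160, count 1 with .3124.

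Look 2 (n = 10): .1160 × .2352 + .3124 × .5716 = .0273 + .1786 = .2058. Cumulative .7774. Carried forward: counts 0, 1, 2 with .0135, .0725, .1366.

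Look 3 (n = 15): .0135 × .0540 + .0725 × .2352 + .1366 × .5716 = .0959. Cumulative .8733.

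Look 4 (n = 20): the same step adds .0505. Cumulative .9238, which reproduces the stated .92.

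**At p = .10.** In a block of 5: P(0) = .5905, P(1) = .3281, P(≥2) = .0815, P(≥3) = .0086.

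Look 1: .0815. Look 2 adds .5905 × .0086 + .3281 × .0815 = .0051 + .0267 = .0318, cumulative .1132. Looks 3 and 4 bring it to .1290 and .1378.

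The stated .10 is therefore not reproduced. It cannot be, because the first two looks alone already exceed it.

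| Patients enrolled | P(stop), 35% | P(miss), 35% | P(stop), 10% |
|---|---|---|---|
| 5 | .57 | .43 | .08 |
| 10 | .78 | .22 | .11 |
| 15 | .87 | .13 | .13 |
| 20 | .92 | .08 | .14 |

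A simulation of 400,000 trials per rate gave .777 (10 patients) and .924 (20 patients) at 35%, and .113 and .137 at 10%. Checking after every patient with the same thresholds gives the same exact values.

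**What would reproduce both stated figures.** A first look at 3 of 5, with the other boundaries unchanged, gives .915 at 35% and .0996 at 10% for 20 patients, which round to .92 and .10. Under that rule, 3 events in the first 5 already imply at least 3 in 10. The 10-patient values are then the single binomial tails P(≥3 of 10) = .738 and .070, that is .74 and .07.

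**The case against.** The strongest reply is that .92 is not an error. It is correct for the 20-patient expansion that 14.3 specifies, and operating characteristics are normally quoted for planned accrual. The Arm C hold is a dated status note, not a redesign. Accrual has since closed, so rewording the rule changes no enrollment decision, and the 51 patients are not split by arm or phase, so the number in expansion cannot be derived. All of this stands, and it limits the point to a missing update with a consequence for reporting. It does not make .92 a property of a 10-patient expansion.

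A second reply concerns scope. A reader might infer from the phrase about both cohorts accruing that the rule was switched off for Arm D. The documents do not support that: the phrase can simply describe when pooled monitoring happens, nothing says the rule lapses if one arm pauses, and the first two boundaries can be applied to 10 Arm D patients as printed. What stands is that the text does not settle the matter.

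A reader might also infer that this is the plan's only binding safety stop. It is not: Sections 9.5 and 14.2 require an arm to be discontinued after 2 or more DLTs in its lowest dose-finding cohort. Section 10.10 also has individual discontinuation rules for many grade 4 toxicities, and institutional monitoring applies. None of these is a cohort-level statistical stop in the expansion phase, but they rule out the broader statement.

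**Conclusion.** The point holds as a restatement of operating characteristics. The stated .92 applies only if all 20 pooled expansion patients are enrolled. With 10, the printed boundaries give .78 at 35%, a loss of about 15 percentage points (.9238 − .7774 = .1464), and the chance of missing a 35% grade 4 rate rises from .08 to .22. The stated .10 is wrong for the printed boundaries at 20 patients, where the value is .14.

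The 10-patient figures assume that Arm C expansion did not reopen; if it partly reopened, the 35% figure lies between .78 and .92. They also assume that the printed boundaries are the intended ones. If the first look was meant to be 3 of 5, the 10-patient values are .74 and .07. The shortfall at 35% remains either way. Which boundary was intended cannot be settled from the documents.

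The practical effect is mainly on what the trial can claim about safety monitoring in the cohort actually enrolled. The documents do not show that the rule was inactive or that Arm D was left without protection.

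**What to change.** In Sections 9.6 and 14.3:

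1. State that the rule counts patients in whichever expansion cohort or cohorts accrue.
2. Reconcile the printed boundaries with the stated .92/.10 pair. If the boundaries stand as printed, restate .10 as .14. If a different first look was intended, say so and recompute.
3. Report the stopping probabilities by number enrolled. As printed, these are .78 (35%) and .11 (10%) for 10 patients, and .92 and .14 for 20.

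Steps 2 and 3 should be done together: printing .11 for 10 patients beside an uncorrected .10 for 20 would be impossible, since added looks cannot lower the cumulative stopping probability. With accrual closed, the study report should give the number enrolled in expansion by arm and say how the rule was applied.

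The cost is wording in two sections and less favorable stated figures. No added patients or assessments are needed.
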